Questions regarding patient eligibility, treatment, dose modifications, protocol, IRB, model consent revisions, site regulatory documents, biospecimen collection, requirements, and processing, etc.	AFT Clinical Research Associates Email: [REDACTED]
Questions related to AE/SAE reporting	Novella Clinical: Safety Management Ph: US Toll Free: [REDACTED] Email: [REDACTED]

Synopsis and Study Schema

Study Title	A Phase I Study of Ibrutinib (PCI-32765) in Combination with Revlimid/dexamethasone (Rd) in Relapsed/Refractory Multiple Myeloma
Study Number	AFT-15
Study Type/Phase	Phase Ib
Clinical Indication	Relapsed/Refractory Multiple Myeloma
ClinicalTrials.gov Identifier	NCT03702725
IND Number	140017
Number of Study Patients	19-25 (Dose escalation:9-18; Dose expansion: 4-10)
Estimated Duration of Trial	Approximately 42 to 48 months to enroll *Patients are treated until disease progression
Rationale	In the last decade, significant progress has been made in the treatment of Multiple Myeloma (MM), primarily due to the introduction of proteasome inhibitors (PI) and immunomodulatory drugs (IMiDs). However, nearly all patients ultimately relapse and require further therapy, making the development of new compounds for MM therapy an important priority. Preclinical studies suggest synergism between lenalidomide and ibrutinib in MM. The anti-myeloma effects of lenalidomide have been previously described and include caspase-8-dependent apoptosis of MM cells, inhibition of angiogenesis, and activation of NK and T effector cells. Both ibrutinib and lenalidomide downregulate IRF4, a master transcriptional factor that mediates myeloma cell survival, and both exert effects on the BM microenvironment with overlapping yet distinct targets that influence MM cell growth and survival. The combination of lenalidomide and ibrutinib is thus an attractive therapeutic strategy not only as a potent anti-MM regimen but also in terms of positively impacting bone disease.

Primary Objective	
 1. To determine the maximum tolerated dose (MTD) in phase I and recommended dose in extension cohort of ibrutinib in combination with lenalidomide and dexamethasone 2. To examine the safety profile of ibrutinib in combination with lenalidomide and dexamethasone
Secondary Objectives	
To determine the following:
 
 1. Progression-free survival (PFS): Time from registration to disease progression or death due to any cause. 2. Overall survival (OS): Time from registration to death due to any cause. 3. Overall Response Rate: Time from start of treatment to objective response 4. Duration of response: Time from documented response to disease progression among those patients whose disease meets the IMWG criteria for disease response
Correlative Science Objectives	To perform select immunologic studies with this combination therapy.
Study Design	
Part 1: Dose Escalation
 
Patients in the dose escalation phase will receive oral treatment with:
 
Ibrutinib: Days 1-28 of every 28-day cycle Lenalidomide: Days 1-21 of every 28-day cycle Dexamethasone: 40 mg for patients <75 at the time of registration 20 mg for patients ≥ 75 at registration on Days 1, 8, 15 and 22 of every Cycle. One cycle is 28 days.
 
Starting doses of ibrutinib and lenalidomide will be assigned at the time of registration. A minimum of 2 or a maximum of 6 patients will be accrued to a given dose level. Doses will not be escalated in any individual patient. If none of the first 3 patients treated at a given dose level develops a DLT during the first cycle of treatment, enrollment to the dose level will be closed and enrollment will reopen at next higher dose level. If there are no other higher dose levels to be tested, three additional patients will be enrolled at the current dose level to confirm MTD. If one of the first 3 patients treated at a given dose level develops a DLT during the first cycle of treatment, three additional patients will be enrolled onto the current dose level. If, at any time in the enrollment of these 3 additional patients, a patient develops a DLT, enrollment will be closed to this dose level. Enrollment will be reopened to the next lower dose level if fewer than 6 patients have been treated at that dose level. If none of these 3 additional patients develops a DLT during the first cycle of treatment, enrollment to this dose level will be closed and enrollment will reopen at next higher dose level. If

	
there are no other higher dose levels to be tested, this will be considered the MTD.
 
Patients will return to the clinic every 28 days for physical exams, laboratory assessments and review of side effects.
 
Patients who do not have disease progression and have not experienced unacceptable toxicities will be eligible to continue protocol treatment at their current dose level until disease progression, unacceptable toxicity, or refusal. Those patients who have not experienced progression of disease but have unacceptable toxicity may be eligible for re-treatment at a lower dose.
 
Part 2: Dose Expansion Once the MTD has been established or determined, 4-10 additional patients will be treated at the MTD of lenalidomide and ibrutinib at the same schedule as above. Dexamethasone will be given at the same dose as in the dose escalation portion of the study.
 
Patients who have not had disease progression and have experienced acceptable toxicity will be eligible to continue protocol treatment at their current dose level until disease progression, unacceptable toxicity, or refusal. Those patients who have not progressed and who have experienced unacceptable toxicity may be eligible for re-treatment at a lower dose. A maximum of 2 reductions are allowed.
 
Criteria for discontinuation of protocol therapy include:
 
• Tumor progression• Request by the patient to withdraw• Unacceptable adverse events• Treatment delay of >4weeks• Intercurrent illness which would, in the judgment of the investigator, affect assessments of clinical status to a significant degree that require discontinuation of drug• Non-protocol chemotherapy, or an experimental drug during the trial 
Patients who discontinue treatment for any of the above reasons will go to survival follow-up. Once a patient has entered the survival follow-up phase of the trial, his/her therapy is at the discretion of the treating physician. Patients' charts will be reviewed for progression and survival endpoints during visits with treating physicians.
 
Bone marrow aspirate will be collected at pre-treatment and at end of cycle 1 for micro-RNA profiling and gene expression for correlative studies.
 
Peripheral blood will be collected at pre-treatment, after cycles 1, 3, 6 and 12 for immunome correlative studies.

--	---

**Inclusion Criteria**

1. Men and women ≥ 18 years
2. Eastern Cooperative Oncology Group (ECOG) performance status of 0–1.
3. Symptomatic MM (as defined by revised IMWG criteria) with measurable disease, defined here as having at least one of the following:
 - Serum monoclonal protein ≥ 0.5 g/dL
 - ≥ 200 mg of monoclonal protein in the urine on 24 hour electrophoresis
 - Serum immunoglobulin free light chain: involved FLC ≥ 10 mg/dL (≥ 100 mg/L) AND abnormal serum immunoglobulin kappa to lambda free light chain ratio
4. At least 1 prior line of therapy with demonstrated disease progression following the most recent line of treatment (induction followed by maintenance or autologous transplant and maintenance, will be considered a line of therapy. Each subsequent change of regimen will be considered a line of therapy)
5. Progression of disease within 60 days of completion of last therapeutic regimen or the failure to achieve minimal response while on last treatment (according to IMWG).
6. Patients should not have progressed on lenalidomide at a dose of more than 10 mg.
7. No prior treatment with ibrutinib or any other protein kinase inhibitory drug or drug targeting the BCR signal transduction pathway.
8. Patients with prior Daratumumab and allogeneic stem cell transplant are included.
9. PT/INR $<1.5 \times$ ULN and PTT (aPTT) $<1.5 \times$ ULN except if on anticoagulation for medical reasons in which case INR should be ≤ 3
10. Adequate hematologic function independent of transfusion and growth factor support for at least 7 days prior to registration, with the exception of pegylated G-CSF (pegfilgrastim) and darbopoeitin (which require at least 14 days prior to screening and enrollment) defined as:
 - Absolute neutrophil count (ANC) $\geq 1000/\text{mm}^3$ independent of growth factor support.
 - Transfusion independent platelet counts $\geq 75,000/\text{mm}^3$ (or $\geq 50,000/\text{mm}^3$ if bone marrow involvement is $\geq 50\%$).

	
 • Hemoglobin level ≥ 8 g/dL, independent of transfusion support. 
11. Biochemical values must be within the following limits within 7 days prior to registration
 
 • Alanine aminotransferase (ALT) and aspartate aminotransferase (AST) $\leq 2.5 \times$ upper limit of normal (ULN). • Total bilirubin $\leq 1.5 \times$ ULN (unless bilirubin rise is due to Gilbert's syndrome or of non-hepatic origin). • Serum creatinine $\leq 2 \times$ ULN or GFR ≥ 30 ml/min based on either the estimated Glomerular Filtration Rate (Crockcroft-Gault) or measured GFR from 24-hour urine sample. Study participants with $30 < \text{GFR} < 60$ will be treated according to manufacturer's instruction with lenalidomide 10mg rather than 25 mg. 
12. Ability to understand and willingness to sign a written informed consent from (ICF).
 
13. Ability to adhere with the study visit schedule and other protocol procedures.
 
14. A negative pregnancy test will be required for all women of child bearing potential within 7 days prior to study treatment start. Breast feeding is not permitted.
 
15. Fertility requirements
 
 • Female patients with child bearing potential must have a negative pregnancy test at least 7 days before starting treatment drugs. • Male subject must use an effective barrier method of contraception during the study and for 3 months following the last dose if sexually active with a female of childbearing potential. • Female patients must be either post-menopausal, free from menses ≥ 2 yrs, surgically sterilized, willing to use two adequate barrier methods of contraception to prevent pregnancy or agree to abstain from sexual activity starting from screening and for 90 days afterwards. • Female patients of child bearing potential must agree to comply with the fertility and pregnancy test requirements dictated by the Rev-Assist program. 
16. Willingness to provide blood and tissue samples for correlative research purposes

--	--

Exclusion Criteria	
 1. Prior history of Polyneuropathy, organomegaly, endocrinopathy, M-protein, and skin changes (POEMS) syndrome, osteosclerotic myeloma, Crow-Fukase syndrome, primary amyloidosis or plasma cell leukemia. 2. Radiotherapy within 21 days of registration. However, if the radiation portal was localized to single lesion or fracture site and covered by $\leq 5\%$ of the bone marrow reserve (by investigator estimate), the subject may be enrolled irrespective of the end date of radiotherapy. 3. Prior chemotherapy: 
 • Alkylators (e.g. melphalan, cyclophosphamide) ≤ 21 days prior to registration and/or monoclonal antibody ≤ 6 weeks prior to first administration of study treatment. • Anthracyclines ≤ 21 days prior to registration. • High dose corticosteroids, immune modulatory drugs (thalidomide), or proteasome inhibitors (bortezomib or carfilzomib) ≤ 14 days prior to registration. 
 ◦ If patient is on current lenalidomide treatment, they may continue on current dose until starting protocol treatment. 4. No concomitant high dose corticosteroids (concurrent use of corticosteroids). EXCEPTION: Patients may be on chronic steroids (maximum dose 10 mg/day prednisone equivalent) if they are being given for disorders other than myeloma, i.e., adrenal insufficiency, rheumatoid arthritis, etc. 5. Currently active, clinically significant cardiovascular disease such as uncontrolled or symptomatic arrhythmias, congestive heart failure, or myocardial infarction within 6 months of registration, or any Class 3 or 4 cardiac disease as defined by the New York Heart Association Functional Classification ($QTcF > 470$ msec). 6. Unable to swallow capsules or disease significantly affecting gastrointestinal function, such as malabsorption syndrome, resection of the stomach or small bowel, or complete bowel obstruction. 7. History of prior malignancy, with the exception of the following: 
 • Malignancy treated with curative intent and with no known active disease present for more than 3 years prior to registration and felt to be at low risk for recurrence by treating physician;
---------------------------	--

	
 • Adequately treated non-melanoma skin cancer or lentigo maligna without current evidence of disease; or • Adequately treated breast or cervical carcinoma in situ without current evidence of disease. 
 8. Peripheral neuropathy Grade > 2 on clinical examination within 14 days prior to registration. 9. Uncontrolled diabetes mellitus. 10. Currently active systemic fungal, bacterial, viral, or other infection not controlled (defined as exhibiting ongoing signs/symptoms related to the infection and without improvement, despite appropriate antibiotics or other treatment). 11. Use of antibiotics for treatment of infection within 14 days prior to registration. 12. Recent infection requiring systemic treatment that was completed within 14 days of registration. 13. Known infection with human immunodeficiency virus (HIV) or active infection with hepatitis C virus (HCV) or hepatitis B virus (HBV) or any uncontrolled active systemic infection. Note: Subjects with known history positive for hepatitis B core antibody, hepatitis B surface antigen, or hepatitis C antibody must have a negative polymerase chain reaction (PCR) result within 14 days prior to registration. 14. History of stroke or intracranial hemorrhage within 6 months prior to registration. 15. Subjects who received a strong cytochrome P450 (CYP3A) inhibitor within 7 days prior to the first dose of ibrutinib or subjects who require continuous treatment with a strong CYP3A inhibitor see (Appendix II) 16. Currently active, clinically significant hepatic impairment. Child-Pugh class B or C according to the Child Pugh classification (Appendix III). 17. Lactating or pregnant. 18. Major surgery within 4 weeks prior to registration. 19. Known bleeding disorders (eg, von Willebrand's disease or hemophilia). 20. Allergies and adverse drug reactions: history of allergy to study drug components.
--	---

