In safety pharmacology assessments, no treatment-related effects were observed in the central nervous system or respiratory system in rats at any dose tested. Further, no treatment-related corrected QT interval (QTc) prolongation effect was observed at any tested dose in a cardiovascular study using telemetry-monitored dogs.

Based on data from rat and dog including general toxicity studies up to 13 weeks duration, the greatest potential for human toxicity with ibrutinib is predicted to be in lymphoid tissues

(lymphoid depletion) and the gastrointestinal tract (soft feces/diarrhea with or without inflammation). Additional toxicity findings seen in only one species with no observed human correlate in clinical studies to date include pancreatic acinar cell atrophy (rat), minimally decreased trabecular and cortical bone (rat) and corneal dystrophy (dog).

In studies in pregnant rats and rabbits, ibrutinib administration was associated with malformations (teratogenicity) at ibrutinib doses that result in approximately 14 and 20 times the exposure (area under the concentration-time curve [AUC]) in patients administered the dose of 560 mg daily and 420 mg, respectively. Fetal loss and reduced fetal body weights were also seen in treated pregnant animals.

For the most comprehensive information regarding nonclinical safety pharmacology and toxicology, please refer to the current IB.

Carcinogenesis, Mutagenesis, Impairment of Fertility

Carcinogenicity studies have not been conducted with ibrutinib. In vitro and in vivo genetic toxicity studies showed that ibrutinib is not genotoxic. No effects on fertility or reproductive capacities were observed in a study in male and female rats.

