 - Serum creatinine $\leq 2 \times$ ULN or GFR $\geq 30 \text{ ml/min}$ based on either the estimated Glomerular Filtration Rate (Crockcroft-Gault) or measured GFR from 24-hour urine sample. Study participants with GFR 30-50 ml/min will be treated according to manufacturer's instruction with lenalidomide 10mg rather than 25 mg.
- 11. Ability to understand and willingness to sign a written informed consent form (ICF).
- 12. Ability to adhere with the study visit schedule and other protocol procedures.
- 13. A negative pregnancy test will be required for all women of child bearing potential within 7 days prior to registration. Breast feeding is not permitted.
- 14. Fertility requirements
 - Female patients with child bearing potential must have a negative pregnancy test at least 7 days before starting treatment drugs.
 - Male subject must use an effective barrier method of contraception during the study and for 3 months following the last dose if sexually active with a female of childbearing potential.

- Female patients must be either post-menopausal, free from menses \geq 2 yrs, surgically sterilized, willing to use two adequate barrier methods of contraception to prevent pregnancy, or agree to abstain from sexual activity starting from screening and for 90 days after lenalidomide treatment
- Female patients of childbearing potential must agree to comply with the fertility and pregnancy test requirements dictated by the Rev-Assist program.

15. Willingness to provide blood and tissue samples for correlative research purposes

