6.2. Pre-Treatment Criteria

A treatment may begin on the scheduled Day 1 of a new cycle if:

- The ANC is $\geq 1,000/\mu\text{L}$;
- The platelet count is $\geq 50,000/\mu\text{L}$;
- Any Ibrutinib or lenalidomide-related allergic reaction/hypersensitivity or sinus bradycardia/ other cardiac arrhythmia adverse event that may have occurred has resolved to \leq grade 1 severity;
- Any other Ibrutinib or lenalidomide-related adverse event that may have occurred has resolved to \leq grade 2 severity.

Laboratory values (excluding Child Pugh score) on Cycle 1, Day 1 must meet eligibility criteria per Section 3.1 (Inclusion Criteria).

6.2.1 Cycle 1 Day 1

Cycle 1 Day 1 hematology and chemistry laboratory assessments will be repeated if not performed within 7 days of starting study treatment.

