9.1.5 Follow-up for Other Malignancies

Occurrences of any new malignant tumors including solid tumors, skin malignancies and hematologic malignancies will be reported throughout study participation, including duration of study treatment and during any protocol specified follow-up periods.

Table 15 **Schedule of Assessment**

Treatment Day → Assessments and Procedures ↓	≤ 14 days prior to registration	Day 1 (all cycles)	Day 15 ± 2 days (all cycles)	End of Cycle 1	End of Cycle 3	End of Cycle 6	At end of treatment or treatment discontinuation
History and exam, weight ^a	X	X	X				X
Height	X						
ECOG Performance Status	X	X	X				X
Adverse event assessment	X	X	X				X
Concomitant Medications	X						X
Hematology group: WBC, ANC, ALC, Hgb, and PLT ^b	X	X	X				X
Chemistry group SGOT AST, total bili, Alk Phos, Creatinine, potassium, calcium, magnesium, phosphorus, sodium, albumin), blood glucose ^b	X	X	X				X
TSH, Free T4 ^{cc}	X						
LDH, Uric Acid ^b	X	X	X				X
Serum pregnancy test ^d	X						
Complete body CT	X	X ^e				X ^e	X ^e
Bone Marrow Biopsy ^f	X			X			
Mandatory blood specimens ^g	X	X ^g		X ^g	X ^g	X ^g	
ECG ^h	X						X

Treatment Day → Assessments and Procedures ↓	≤ 14 days prior to registration	Day 1 (all cycles)	Day 15 ± 2 days (all cycles)	End of Cycle 1	End of Cycle 3	End of Cycle 6	At end of treatment or treatment discontinuation
Serum Immunoglobulins, monoclonal protein and free light chain; beta 2 microglobulin ⁱ	X						X

- a. History, exam, and weigh will be done on day 1 of subsequent cycles after cycle 2
- b. Labs will be done weekly for the first 2 cycles, then on day 1 of subsequent cycles
- c. TSH and Free T4 at screening and every 2 cycles
- d. To be performed within 7 days of receiving drug.
- e. If clinically indicated for those with extramedullary disease indicated on baseline CT at completion of cycle 6 (cycle 6 day 28 ±3 days) or to confirm CR
- f. 2 tubes of 5 ml each of bone marrow aspirates in green tube (2) to be collected pre-treatment (prior to start of cycle 1) and at end of cycle 1 (prior to start of cycle 2).
- g. 15 ml peripheral blood to be collected prior to start of treatment and at end of cycles 1, 3, and 6 for the immunome correlate
- h. ECG should be performed within 14 days prior to registration and end of treatment, and as needed during the course of the study.

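### The pregnancy-test criteria set opposite 7-day limits before first dose, so the one scheduled test satisfies both only on day 7

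*Combined protocol and SAP*

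**What the plan says.** The timing of the pregnancy test is stated in five places.

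- Synopsis, Inclusion Criteria, item 14: "A negative pregnancy test will be required for all women of child bearing potential within 7 days prior to study treatment start".
- Synopsis, Inclusion Criteria, item 15, first bullet: "Female patients with child bearing potential must have a negative pregnancy test at least 7 days before starting treatment drugs".
- Section 3.1, item 13: "A negative pregnancy test will be required for all women of child bearing potential within 7 days prior to registration".
- Section 3.1, item 14, first bullet: the same sentence as Synopsis item 15.
- Table 15, row "Serum pregnancy test": one mark, in the pre-registration column, with footnote d: "To be performed within 7 days of receiving drug".

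Two further provisions bear on it. Section 6.2.1 has a repeat rule limited to other tests: "Cycle 1 Day 1 hematology and chemistry laboratory assessments will be repeated if not performed within 7 days of starting study treatment". Section 3.1 item 14 also refers to an outside program: "Female patients of childbearing potential must agree to comply with the fertility and pregnancy test requirements dictated by the Rev-Assist program". The documents do not give that program's test dates.

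**The concern.** Two adjacent Synopsis criteria use the same starting point, treatment start, and point in opposite directions: one caps the age of the test at 7 days and the other requires it to be at least 7 days old. The main text repeats the minimum in Section 3.1 and the maximum in Table 15, so neither part of the protocol corrects the other.

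These are operative rules. Section 5 has site staff confirm before enrollment that every eligibility criterion was met in its stated time window, and Section 15.6 says the sponsor grants no waivers for deviations. Read literally, almost any single test could be logged as an eligibility deviation.

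The safety purpose calls for a recent test, and the minimum-age wording asks for an older one. Section 1.4.1.1 reports that "In studies in pregnant rats and rabbits, ibrutinib administration was associated with malformations (teratogenicity"), at about 14 and 20 times patient exposure, and Section 1.1.2 describes lenalidomide as a thalidomide analogue.

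**Working it through.** No sample-size, power or error-rate figure is involved. The check is to intersect the stated windows.

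**Notation.** Let *a* be the age of the test in whole days at first dose, and *g* the days from registration to first dose. Footnote d is read as meaning before drug, since its mark sits in the pre-registration column.

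**Inputs**

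| Source | Counted from | Condition |
|---|---|---|
| Synopsis item 14 | treatment start | 0 ≤ a ≤ 7 |
| Synopsis item 15 | treatment start | a ≥ 7 |
| Section 3.1 item 13 | registration | g ≤ a ≤ g + 7 |
| Section 3.1 item 14 | treatment start | a ≥ 7 |
| Table 15 footnote d | receipt of drug | 0 ≤ a ≤ 7 |

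**Step 1: Synopsis items 14 and 15.** a ≤ 7 and a ≥ 7 leave a = 7 only. If *within 7 days* were read as strictly fewer than 7, no day would remain.

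**Step 2: Section 3.1 item 14 and footnote d.** These are the same two inequalities, so again a = 7 only.

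**Step 3: Section 3.1 items 13 and 14 on their own.** The condition is max(7, g) ≤ a ≤ g + 7. The documents state no limit on *g*, so these values are illustrative:

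| g (days) | Ages allowed by items 13 and 14 | Also meeting footnote d |
|---|---|---|
| 0 | 7 | 7 |
| 1 | 7–8 | 7 |
| 3 | 7–10 | 7 |
| 7 | 7–14 | 7 |
| 8 | 8–15 | none |
| 10 | 10–17 | none |

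Items 13 and 14 do not conflict with each other; the conflict in the main text is between item 14 and footnote d. But because item 13 counts from registration, Section 3.1 alone sets no fixed maximum age at first dose. Once *g* exceeds 7, no single test can meet both item 13 and footnote d.

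**Step 4: does the repeat rule help?** Section 6.2 requires Cycle 1 Day 1 laboratory values to meet Section 3.1. Section 6.2.1, which triggers a repeat when results are more than 7 days old at first dose, names hematology and chemistry but not the pregnancy test.

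**Step 5: after correction.** With every limit written as *within 7 days before treatment start*, the condition is 0 ≤ a ≤ 7. That allows 8 whole-day values (0 to 7) instead of one, and every permitted test is recent.

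**The case against.** The strongest reply is that no criterion says the same test must meet both limits. One test taken 7 or more days before dosing and a second within 7 days would satisfy Synopsis items 14 and 15 in full. The Rev-Assist reference makes more than one test plausible. On that view item 15 could be the first of two tests, and rewriting it would remove a safeguard. A single mark in Table 15 is also weak evidence of a single test, because the TSH/free T4 and immunoglobulin rows have further tests that appear only in their footnotes.

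Part of this stands. Two tests would satisfy both texts, so the conflict applies to a single test. It does not remove the problem. Footnotes c and i add further time points for their rows, whereas footnote d adds none and dates the one scheduled test within 7 days of drug. If two tests are intended, the protocol needs to say so and schedule the second. Because the REMS schedule is not given, the reference to it cannot show which written limit applies. A fix that expressly keeps any REMS tests loses no safeguard.

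It is also fair to say that footnote d already caps the test age, so the wider ranges in Step 3 describe tests that footnote d would reject. They show what a site would accept if it worked from Section 3.1 alone.

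Finally, the consequence is limited. Exclusion 17 bars pregnant patients, Section 11.2.6 requires full REMS compliance, and Table 13 holds therapy when pregnancy is suspected. That is accepted and is reflected in the rating.

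**Conclusion.** The inconsistency is real and is in the current text of both the Synopsis and the main protocol. The permitted ages at first dose are 7 days or more under one set of provisions and 0 to 7 days under the other, with one day in common.

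The rating is minor. It concerns only women of childbearing potential among the planned 19 to 25 patients, and the documents do not give their number. It touches no DLT rule, sample size or analysis. The exposure multiples describe a hazard in animals; they do not show that this wording would lead to exposure in pregnancy.

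The conclusion rests on reading Table 15 as scheduling one test, on including day 7 in *within 7 days*, and on reading footnote d as before drug. That *at least* was written in error for *within* is likely but is an inference; the conflict exists either way.

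**What to change.** 1. In Synopsis item 15 and Section 3.1 item 14, first bullet, change *at least 7 days before* to *within 7 days before* starting treatment.
2. In Section 3.1 item 13, count the 7 days from study treatment start, to match Synopsis item 14 and Table 15 footnote d.
3. In Section 6.2.1, add the pregnancy test to the assessments repeated when more than 7 days old at first dose.
4. State that any additional pregnancy tests required by the REMS program also apply. If the sponsor does intend two protocol tests, say so and add the second to Table 15.

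Apart from that two-test alternative, the cost is three changed phrases and two short additions. No new scheduled visit is needed.
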